2.8.3.1.3 Olink T48

Olink T48 cytokines data panel will be provided as pg/ml values. Cytokines of interest will be analyzed as described for blood biomarkers.

2.8.3.1.4 [REDACTED]

[REDACTED]

[REDACTED]

2.8.3.2 *Pharmacodynamic assessment*

The following analyses will be performed on the biological-naïve participant of the biomarker PD population of Period A.

A mixed-effect model with repeated measures (MMRM) will be used to assess overall treatment effect on biomarker fold change from baseline (IL-6, sTNF, sOX4OL, CXCL13, YKL40, Absolute neutrophil count, CRP, hs-CRP, SAA, ASCA, ACPA, ESR and Lipocalin-2). A log₂ transformation will be applied. All post-baseline data until Week 16/EOT will be considered. The model will include the fixed categorical effects of study intervention group (SAR442970 vs placebo), visit and intervention-by-visit interaction, as well as the continuous fixed covariate of baseline biomarker value and will consider a participant-level random effect.

$\log_2(1 + \text{Fold Change}) \sim \text{baseline value} + \text{time} + \text{treatment} + \text{time*treatment} + (1 | \text{subjectID})$

The Restricted Maximum Likelihood (REML) method will be used to estimate the variance of the parameters of the MMRM.

The point estimate of the biomarker change at a given time point, with the corresponding 90% confidence intervals will be reported as percent change from baseline.

$$\text{Percent change from baseline} = 100(FC - 1)$$

Where the baseline value will be the median biomarker value at baseline across all patients, and time and treatment will be fixed for each treatment group.

The estimated percent change from baseline for all visits and treatment groups will be reported in a table.

Additionally a boxplot of the percent change from baseline of biomarker level at Week 16 vs. HiSCR50 response at Week 16 by study intervention group will be provided in the biomarker PD population of Period A.

2.8.3.3 *Correlation between biomarkers and primary efficacy endpoint*

This analysis aims to evaluate the predictive performance of biomarkers for the primary efficacy endpoint: HiSCR50 at Week 16.

For numerical biomarkers of interest, a boxplot of the biomarker level at baseline by HiSC50 response at Week 16 in the predictive population of Period A

The baseline biomarker data might be included in a binary logistic regression model with responders/non responders as endpoint (response defined by the HiSCR50 criteria), defined across different treatment intervention groups. For this analysis, the resulting odds ratio and the corresponding 90% confidence interval will be reported.

Outputs not included into the CSR might also include a heatmap visualization of all biomarkers except transcriptomic data reported on a separate heatmap. For a multivariate predictive analysis, all baseline biomarkers will be included into a multivariate logistic model with elastic net penalization. A 10-fold cross-validation will be conducted; ROC curve; AUC and selected predictive biomarker set will be reported.

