1.1 STUDY DESIGN

This is a multinational, randomized, placebo-controlled, double-blind, Phase 2a proof-of-concept study. The purpose of this study is to evaluate the efficacy, safety, PK, biological effects of SAR442970 compare with placebo in adult participants with moderate to severe hidradenitis suppurativa (HS).

The study is composed of 3 parts: a double-blind, placebo-controlled period (Period A), followed by an open-label period (Period B), and then a safety Follow-up Period (Period C). After a screening period of 2 to 4 weeks, participants will receive SAR442970 150 mg or matching placebo Q2W at the Week 0 visit up to the Week 14 visit as part of Period A. Beginning at the Week 16 visit, all participants will receive SAR442970 150 mg Q2W up to the visit prior to the individual participant's end of treatment (EOT) visit as part of Period B. Period C will commence with the End of Treatment (EOT) visit and conclude with the End of Study (EOS) visit. For participants in the US, response will be assessed at the Week 20 visit (see definition of response in [Section 2.2.1](#)). Responders at Week 20 will continue in Period B to complete the 12-week open-label period. Non-responders at Week 20 will move directly to the safety follow-up period (Period C) with the Week 20 visit serving as their EOT visit.

Approximately 84 participants will be randomized in a 2:1 ratio to SAR442970 150 mg Q2W or matching placebo. Randomization will be stratified by HS treatment history (biologic and small molecule immunosuppressive-naïve or TNF-experienced) and Hurley stage (II or III). The recruitment target is approximatively 66 biologic and small molecule immunosuppressive-naïve and approximatively 18 TNF-experienced. Within the biologic and small molecule immunosuppressive-naïve subgroup, the number of participants with Hurley Stage III is not to exceed more than 50%. Within the biologic and small molecule TNF-experienced subgroup, the number of participants with Hurley Stage III is not to exceed more than 50%.

The primary analysis population is the biologic and small molecule immunosuppressive-naïve subgroup. Efficacy objectives and endpoints will be evaluated in an exploratory manner in the TNF-experienced subgroup.

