2.2.2 Main analytical approach

The primary endpoint will be analyzed with the primary estimand defined according to the following attributes:

- Endpoint: Percentage of participants achieving HiSCR50 at Week 16.
- Treatment condition: SAR442970 will be compared to Placebo.
- Analysis population: Biologic and small molecule immunosuppressive-naïve population of Period A.
- Intercurrent events (IE):

The following intercurrent events will be handled with the composite variable strategy; participants will be considered as non-responders after such IE:

- Starting or increase in dose of oral antibiotic therapy for HS prior to Week 16
- Starting selected prohibited medications. Participants that receive the selected treatment listed in [Table 5](#) will be reviewed in a blinded fashion to make sure the medication was used due for HS treatment failure and not an unrelated condition.
- Discontinuation of study intervention due to lack of efficacy

The following IEs will be handled with the treatment policy strategy (without IEs that need to be handled with composite variable strategy). Data collected after starting such IE will be included:

- Starting other prohibited medications

- Discontinuation of study intervention due to reasons other than lack of efficacy
- Population-level summary: A Bayesian logistic regression model including intervention group and stratified by baseline Hurley Stage will be used with an informative prior on the placebo response rate based on the historical studies available. Participant with missing data will be imputed as non-responders. Descriptive statistics will be presented by treatment group.

Table 5 - Selected prohibited and/or rescue medications and procedures impact on efficacy

Endpoints	Intervention (Intercurrent Event)	Intervention in the main statistical analysis (Yes/No) ^a / Selection criteria

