2.3.1 Time to onset of achieving HiSCR50

The time to onset of achieving HiSCR50 by Week 16 will be defined as [date of first time achieving HiSCR50 - date of randomization] in days.

The estimand for time to event endpoint defined in [Table 3](#) will be used. The following IEs will be handled with the composite variable strategy; participants will be censored at Week 16:

- Starting or increase in dose of oral antibiotic therapy prior to Week 16
- Starting selected prohibited medications prior to Week 16. Participants that receive the selected treatment [Table 5](#) will be reviewed in a blinded fashion to make sure the medication was used due for HS treatment failure and not an unrelated condition
- Discontinuation of study intervention due to lack of efficacy

The following IEs will be handled with the treatment policy strategy (without IEs that need to be handled with composite variable strategy). Data collected after starting such IE will be included.

- Starting other prohibited medications
- Discontinuation of study intervention due to reasons other than lack of efficacy

Participants discontinuing the study follow-up before Week 16 will be censored at the time of their last HS clinical parameters assessment.

Comparison of treatment response (SAR442970 vs Placebo) will be summarized using the Cox proportional hazards model, including intervention groups, and stratified by baseline Hurley Stage. The hazards ratios and the 80% and 90% confidence intervals. Kaplan-Meier curves along with associated summary statistics will be provided by intervention group.

2.3.2 Absolute change from Baseline in IHS4 at Week 16

The IHS4 is a validated tool to assess HS severity. The determination of IHS4 requires counting inflammatory nodules, abscesses and draining tunnels and multiplying each by a specific coefficient making it straightforward to apply in both research and clinical practice and easy to use in conjunction with the HiSCR50. A continuous IHS4 score can be derived based on this weighted score. A categorial IHS4 score can also be derived from the weighted score: a total score of 3 or less signifies mild, 4 to 10 signifies moderate, and 11 or higher signifies severe disease.

Two IHS4 scores are to be derived from the primary continuous IHS4. The first one is defined as the improvement by at least one IHS4 stage at Week 16 and the second which is also known as IHS4-55 is defined as a 55% reduction in IHS4 score from Baseline.

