The change from baseline in the IHS4 score at Week 16 will be analyzed using the ANCOVA model including the baseline value, intervention group and baseline Hurley Stage.

The estimand for continuous endpoints defined in [Table 3](#) will be used. The IE handling is as follow:

- Data of participants starting or increasing the dose of oral antibiotic therapy for HS during the treatment period or started selected prohibited medication listed in [Table 5](#) or discontinued study intervention because of lack of efficacy will be excluded after such IE, and participant's worst postbaseline value on or before the time of the IE will be used to assign the endpoint value (WOCF). Participants with no post-baseline value, the baseline value will be used. Participants that receive the selected treatment listed in [Table 5](#) will be reviewed in a blinded fashion to make sure the medication was used due for HS treatment failure and not an unrelated condition.
- For participants who started other prohibited medication or discontinue the treatment prematurely due to other reasons than efficacy, all data collected after the event will be used in the analysis.

Missing data at Week 16 will be imputed with participant worst postbaseline value. For participants with no post-baseline value, the baseline value will be used.

The least square (LS) means of the absolute change from baseline to Week 16 in IHS4 per study invention group will be reported. The difference of SAR442970 against placebo in LS means and the corresponding 80% and 90% confidence intervals will be reported. Descriptive statistics will also be provided.

2.3.3 HS Skin Pain NRS at Week 16

The HS-Skin Pain NRS is a unidimensional numeric rating scale (NRS) that allows for rapid measure of skin pain that can be administered multiple times with minimal administrative burden. The HS-Skin Pain NRS is scored on a 0 to 10 scale with 0 indicating “no skin pain” and 10 indicating “worst skin pain possible”. The HS-Skin Pain NRS has a 24-hour recall period and will be completed as a daily diary, ideally at the same time each day (evening) throughout the Treatment Period.

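### The pharmacodynamic biomarker model omits the Hurley stage randomisation stratum that the other Period A treatment comparisons include, so its between-arm contrast may lose a little precision

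*SAP*

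**What the plan says.** SAP 1.1 states the allocation scheme: "Randomization will be stratified by HS treatment history (biologic and small molecule immunosuppressive-naïve or TNF-experienced) and Hurley stage (II or III"). In the naïve population treatment history is constant, so Hurley stage is the only stratification factor left.

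The specified Period A efficacy comparisons in that population all account for it:
- Primary analysis (SAP 2.2.2): "A Bayesian logistic regression model including intervention group and stratified by baseline Hurley Stage will be used".
- Frequentist version of the primary analysis (SAP 2.2.3) and the skin pain endpoint (SAP 2.3.3): CMH stratified by baseline Hurley stage.
- Time to HiSCR50 (SAP 2.3.1): "Cox proportional hazards model, including intervention groups, and stratified by baseline Hurley Stage".
- Change in IHS4 (SAP 2.3.2): "ANCOVA model including the baseline value, intervention group and baseline Hurley Stage".
- Week 16 exploratory efficacy endpoints (SAP 2.4.3): same approach as the secondary endpoints, with one descriptive exception.

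The pharmacodynamic model (SAP 2.8.3.2) does not: "The model will include the fixed categorical effects of study intervention group (SAR442970 vs placebo), visit and intervention-by-visit interaction". Its remaining terms are baseline biomarker value and a participant random effect, and the displayed formula agrees with the prose. The output specified is the percent change from baseline, with 90% confidence intervals, tabulated by visit and treatment group. No interval for the difference between arms is specified.

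**The concern.** When allocation is balanced within a stratum and that stratum predicts the outcome, a model that ignores it leaves between-stratum variation in the error term. The standard error of the arm contrast is then overstated. The stated purpose of this model is to assess treatment effect, which is a between-arm question.

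A prognostic role for Hurley stage is plausible. It is the trial's own severity stratum, Protocol 4.2 lists it among factors thought to relate to response to adalimumab, and several of the markers are inflammatory (CRP, hs-CRP, SAA, IL-6, neutrophil count). What would be at stake is some precision in the exploratory evidence of pharmacodynamic effect, and consistency with the way the rest of Period A is analysed.

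**Working it through.** **The plan's own figures.** The documents state no precision figure for the biomarker model. The only one given is for HiSCR50: an 80% credible interval half-width below 0.145 with 66 naïve participants (Protocol 9.5). With 44 and 22 participants, the Beta(2.1; 4.9) placebo prior of SAP 2.2.2, a vague prior on active, a 30% placebo rate and assumed active rates of 42% to 70%, the half-width is 0.138 to 0.144. That figure therefore reproduces, but it says nothing about the biomarkers.

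**Inputs from the documents**
- Allocation: "Approximately 84 participants will be randomized in a 2:1 ratio to SAR442970 150 mg Q2W or matching placebo".
- Sizes: "The recruitment target is approximatively 66 biologic and small molecule immunosuppressive-naïve and approximatively 18 TNF-experienced". At 2:1, 66 gives 44 and 22.
- Hurley mix: "the number of participants with Hurley Stage III is not to exceed more than 50" percent. The mix is capped but not fixed.

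**Assumed inputs**
- R², the share of between-participant variance, after baseline biomarker, that Hurley stage explains: 2% to 15%.
- ρ, the intraclass correlation: 0.5, with 1 as the limit of negligible within-participant variation.

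**Formula.** At a single visit the variance is the between-participant part plus the within-participant part. A covariate fixed in time reduces only the first. Relative width of the unadjusted interval for the arm contrast = 1/√(1 − ρR²).

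| R² | ρ = 0.5 | ρ = 1 |
|---|---|---|
| 0 | 0% | 0% |
| 2% | 1/√0.990: +0.5% | 1/√0.98: +1.0% |
| 5% | 1/√0.975: +1.3% | 1/√0.95: +2.6% |
| 10% | 1/√0.950: +2.6% | 1/√0.90: +5.4% |
| 15% | 1/√0.925: +4.0% | 1/√0.85: +8.5% |

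A contrast averaged over visits falls between the columns. SAP 2.8.3 schedules three post-baseline samples per marker up to Week 16. With complete data and ρ = 0.5, the between-participant share becomes 0.5/(0.5 + 0.5/3) = 0.75, so R² of 15% gives 1/√(1 − 0.75 × 0.15) = 1/√0.8875, or +6.1%.

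**Cost of the extra term.** Residual degrees of freedom go from 63 to 62 (66 participants; intercept, arm and baseline value already fitted). If Hurley stage has no effect, the adjusted interval is wider by 0.02%.

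**Simulation check.** A single-visit ANCOVA approximation was simulated with 44 and 22 participants, 2:1 within stratum, 6,000 runs per scenario. Here R² is the share of the whole single-visit residual variance, so it corresponds to the ρ = 1 column.
- Arm contrast: the width ratio of unadjusted to adjusted was 1.00 at R² = 0, about 1.03 at 0.05 to 0.06, 1.06 to 1.07 at 0.11 to 0.12, and 1.11 to 1.12 at 0.18 to 0.20. Coverage of the unadjusted 90% interval rose from 0.90 to about 0.93.
- Arm mean, with the Hurley mix left random as in the design: coverage of the unadjusted interval stayed at 0.90 to 0.92. Coverage of the adjusted interval fell to about 0.88 when Hurley stage was strongly prognostic.

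**The case against.** A reader might infer that the 90% intervals in SAP 2.8.3.2 are wider than the design supports. The documents do not support that, for two reasons. The specified intervals are for each arm's percent change, and because the design balances Hurley stage between arms without fixing its overall mix, the unadjusted per-arm interval is close to nominal. The loss of precision also requires Hurley stage to predict biomarker change after the participant's own baseline value is in the model, and no passage shows this. It is least plausible for markers such as ASCA, ACPA and soluble OX40L; the last was below the quantitation limit in every single-dose sample in healthy volunteers (Protocol 2.2.1.2.1).

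It is also fair to say that no commitment is broken. Protocol 9.2.2.2 and 9.2.3 promise Hurley adjustment for the primary and main secondary endpoints, not for biomarkers. Protocol 8.8 calls the soluble biomarker work exploratory. SAP 2.8.3.2 specifies no test, and SAP 2.6 applies no multiplicity rule.

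All of that stands, and it limits the point to a conditional, small loss on a contrast that the SAP does not yet report. It does not explain why the one stratum relevant to this population is dropped from a model meant to assess treatment effect.

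**Conclusion.** The omission is real and unexplained, and it differs from the other specified Period A treatment comparisons. Its effect is conditional and small: for the between-arm contrast at a visit, about 0.5% to 4% extra width at ρ = 0.5, up to 1% to 8.5% if within-participant variation is negligible, and none if Hurley stage is not prognostic. Both R² and ρ are assumed. The error is in the conservative direction, no bias follows, and the primary analysis is untouched. This is a worthwhile tidying of the SAP rather than a threat to any conclusion.

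**What to change.** In SAP 2.8.3.2, add baseline Hurley stage (II or III) as a fixed effect: `baseline value + Hurley stage + time + treatment + time*treatment + (1 | subjectID)`. If it is left out on purpose, give the reason. Report the SAR442970-versus-placebo contrast at each visit with its 90% confidence interval alongside the per-arm percent changes, and state that the per-arm estimates are averaged over the observed Hurley distribution.

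The cost is one model term, one degree of freedom and a small programming change. Hurley stage is already recorded for every randomised participant. One drawback should be noted in the text: the adjusted per-arm intervals are conditional on the observed Hurley mix, so they may be slightly narrow if read as unconditional intervals for the arm means.

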2.8.3.1 Biomarkers-specific analyses

2.8.3.1.1 Blood biomarkers

Analysis of blood biomarkers will be performed for markers associated with HS and/or SAR442970 activity, including:

- sTNF (soluble Tumor Necrosis Factor)
- sOX40L (soluble OX40 Ligand)
- Lipocalin-2
- CRP (C-Reactive Protein)
- hsCRP (High-Sensitivity C-Reactive Protein)
- SAA (Serum Amyloid A)
- ASCA (Anti-Saccharomyces cerevisiae antibodies)
- ACPA (Anti-Citrullinated Protein Antibodies)
- Absolute neutrophil count
- ESR (Erythrocyte Sedimentation Rate)
- IL-6 (Interleukin-6)
- CXCL13 (C-X-C Motif Chemokine Ligand 13)
- YKL40

For all the blood biomarkers,

- descriptive statistics at baseline and under treatment (table),
- boxplots and/or time profile plots (means \pm SEM)

will be reported by the study intervention group at each visit in both Periods A and B. Both the raw analysis values, change and percent change from baseline will be reported. Data will be log-transformed as appropriate.

Additionally, for period B, fold change, percent change, and absolute change from Week 16 to Week 28 will be calculated for all biomarkers mentioned above. These analyses will compare participants from period A and B. Also, for sTNF and sOX40L, fold change, percent change, and absolute change from Week 16 to Week 36 will also be presented for both groups of participants.

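### The pharmacodynamic biomarker model is meant to assess the treatment effect, but SAP 2.8.3.2 specifies only arm-level changes from baseline and no SAR442970-versus-placebo contrast

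*SAP*

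**What the plan says.** SAP 2.8.3.2 (Pharmacodynamic assessment) applies a mixed model for repeated measures to 13 biomarkers in the naïve participants of the Period A biomarker PD population.

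- **Aim.** The model "will be used to assess overall treatment effect on biomarker fold change from baseline".
- **Terms.** "The model will include the fixed categorical effects of study intervention group (SAR442970 vs placebo), visit and intervention-by-visit interaction", plus the baseline biomarker value and a participant random effect.
- **Scale.** "A log₂ transformation will be applied"; the model formula gives the response as log2(1 + Fold Change).
- **Estimate.** Percent change from baseline, 100(FC - 1), with a 90% CI: "The point estimate of the biomarker change at a given time point, with the corresponding 90% confidence intervals will be reported as percent change from". It is predicted at the median baseline value, where "time and treatment will be fixed for each treatment group".
- **Display.** "The estimated percent change from baseline for all visits and treatment groups will be reported in a table".

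The section also plans a boxplot of Week 16 change by HiSCR50 response and arm. SAP 2.8.3.1.1 adds descriptive statistics and plots that "will be reported by the study intervention group at each visit in both Periods A and B". Neither section names a between-arm estimate, an interval for one, or a test of the treatment or interaction term for Period A.

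**The concern.** The model contains the randomised comparison, but the listed outputs stop at each arm's own change. A within-arm interval that excludes no change shows that the marker moved over time, and does not show that the drug moved it. Some movement common to both arms is plausible, because Protocol 5.1 selects participants on a screening CRP and a baseline lesion count. The documents do not say how large it might be.

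Without a specified contrast, the reader has to compare two intervals by eye. With twice as many participants on SAR442970, its interval is the narrower one, so the comparison leans toward the drug even when the true changes are equal. Leaving the contrast open also leaves the visit, the scale and the meaning of an overall effect to be chosen after unblinding, across 13 markers. At stake is the pharmacodynamic statement in the study report.

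**Working it through.** **Step 1. Compare the aim and outputs with the rest of the SAP.**

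| SAP section | Method | Between-arm quantity named |
|---|---|---|
| 2.2.3 | CMH | treatment difference, 80% and 90% CIs |
| 2.3.1 | Cox model | hazard ratio, 80% and 90% CIs |
| 2.3.2 | ANCOVA | difference in LS means, 80% and 90% CIs |
| 2.3.3 | CMH | treatment difference, 80% and 90% CIs |
| 2.3.4.2 | proportions | difference in response rates, 80% and 90% CIs |
| 2.8.3.2 | repeated-measures model | none |

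Where the SAP intends description only, as in 2.5 and 2.7, it says so. Section 2.8.3.2 does not.

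**Step 2. Illustrate what reading the two intervals side by side would do.** The plan states no SD, effect size or power for this analysis, so there is no figure of its own to reproduce.

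Inputs from the SAP: about 66 naïve participants randomised 2:1 (SAP 1.1), so 66 × 2/3 = 44 and 66 × 1/3 = 22; 90% intervals, so z = 1.645.

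Assumptions: all are evaluable (36 versus 18 as a lower case); one visit; a normal approximation with known SD; no drug effect; the same true change d, in SD units, in both arms.

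Half-widths:
- SAR442970: 1.645/√44 = 0.248 SD
- Placebo: 1.645/√22 = 0.351 SD
- Contrast: 1.645 × √(1/44 + 1/22) = 0.43 SD (0.47 SD for 36 versus 18)

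The chance that an arm's interval excludes no change is P(n) = Φ(-1.645 - d√n) + 1 - Φ(1.645 - d√n). The arms are independent, so the chance that only the SAR442970 interval does so is P(44) × [1 - P(22)].

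| Shared change d (SD) | SAR442970 excludes | Placebo excludes | Only SAR442970 excludes | Contrast excludes zero |
|---|---|---|---|---|
| 0 | 10.0% | 10.0% | 9.0% | 10% |
| 0.2 | 37.7% | 24.5% | 28.4% | 10% |
| 0.3 | 63.5% | 40.7% | 37.7% | 10% |
| 0.5 | 95.3% | 75.8% | 23.0% | 10% |
| 0.8 | 100.0% | 98.2% | 1.8% | 10% |

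At d = 0.3 the opposite pattern, only placebo excluding no change, has probability 0.407 × (1 - 0.635) = 14.9%. With 36 versus 18, the SAR442970-only figure at d = 0.3 is 36.1%.

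**Step 3. Check whether a contrast on the planned scale has a simple meaning.** Take the same ratio of fold changes, 0.8, at two placebo levels.

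- Placebo FC 1, SAR442970 FC 0.8: log2(1.8) - log2(2) = -0.152
- Placebo FC 0.5, SAR442970 FC 0.4: log2(1.4) - log2(1.5) = -0.100

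The same ratio gives two different differences, so a difference on log2(1 + Fold Change) cannot be back-transformed to a ratio of fold changes. On log2(Fold Change) both cases give log2(0.8) = -0.322.

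**Step 4. The word overall.** With an intervention-by-visit term, the treatment effect can differ at each visit, and the treatment coefficient alone depends on how visit is coded. The section does not say whether the effect of interest is at Week 16, averaged over visits, or something else.

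**The case against.** The strongest reply is that the randomised comparison is already in the model, both arms are tabulated at every visit, and the omission concerns display only. A good part of this stands.

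- A reader might infer that SAR442970 is never compared with placebo. The documents do not support that: the treatment and interaction terms are fitted and the placebo estimates sit beside the SAR442970 estimates.
- A reader might also infer that a change common to both arms would be reported as a drug effect. The SAP states no such rule, threshold or test, and a shared change would be visible in the table. The probabilities above belong to an informal reading that the SAP leaves open but does not prescribe.
- It is tempting to size the shared change from the 30% mean of the placebo HiSCR50 prior in SAP 2.2.2. That prior describes a lesion-count response, and nothing in the documents links it to a change in a serum marker. Nor need all 13 markers fall: Protocol 2.2.1.2.1 reports that total TNF rose after dosing.
- The illustration uses one visit and a simple normal model, without the baseline adjustment and repeated visits of the planned analysis.
- The analysis is of limited weight. Protocol 8.8 calls the soluble-biomarker work exploratory, and the primary and secondary efficacy analyses state their own contrasts.

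The gap itself remains. A section that announces a treatment effect, fits a model for it and attaches confidence intervals should say which between-arm quantity it will report.

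**Conclusion.** The point holds as a mismatch between aim and output: SAP 2.8.3.2 sets out to assess a treatment effect and specifies only arm-level percent changes with 90% CIs. The risk is informal comparison of within-arm intervals with half-widths in the ratio √(44/22) = 1.41, not a built-in false claim.

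The direction follows from the 2:1 allocation. The size depends on an assumed shared change: the SAR442970-only pattern occurs in 28%, 38%, 23% and 2% of trials at 0.2, 0.3, 0.5 and 0.8 SD, against 10% for the contrast throughout. The SDs, the shared change and full evaluability are assumptions that the documents neither give nor contradict. Primary and secondary efficacy conclusions are not affected.

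**What to change.** In SAP 2.8.3.2:

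1. Specify the SAR442970-versus-placebo contrast at each post-baseline visit with its 90% CI. Name Week 16 as the main one, or define the overall effect explicitly.
2. State the scale. Either model log2(Fold Change), so that the contrast back-transforms to a ratio of geometric mean fold changes, or keep log2(1 + Fold Change) and define the contrast as a difference in back-transformed percent changes with a stated interval method, such as the delta method or a bootstrap.
3. Label the arm-level percent changes as descriptive and base treatment-effect statements on the contrast only.

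The cost is a few sentences of SAP text, one set of contrasts per biomarker, and either a small change to the response variable or an added interval method. No new data are needed. The downside is a wider interval: 0.43 SD half-width for the contrast against 0.25 SD for the SAR442970 arm alone, under the assumptions above.
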